## 8.10 Comparison with PEDAP Historical Control

974 Results from this PEDAP-AI study will be compared with those from a sample of participants from the 975 prior PEDAP study. For this analysis, participants from the prior PEDAP study will be limited to those who were using MDI before initiating use of the study pump, and whose baseline HbA1c values are no 976

more than 0.2 percentage points outside of the range observed among the PEDAP-AI participants. These 977

- 978 comparisons will be restricted to a follow-up period of approximately two weeks. For PEDAP-AI
- 979 participants, this will be the period from the adjustment of pump settings at the 6-Week visit until the
- beginning of the day of the 8-Week visit. For the PEDAP historical control group, the follow-up metrics 980
- will be calculated from RCT study phase data for those who were assigned to the CLC group, and 981
- Extension phase data for those who were assigned to the SC group. In either case, follow-up data will 982
- come from the 14 days prior to the 56th day after the date of closed loop initiation. 983
- Comparisons between the PEDAP-AI group and the PEDAP historical control group will be made for all 984 985 of the hierarchical and secondary efficacy endpoints listed in section 8.4.2. Continuous endpoints will be
- compared between the PEDAP-AI and PEDAP cohorts using a linear model adjusting for the baseline 986

value, age at initiation of closed loop use, and clinical center as fixed effects. Binary endpoints will be

compared using a logistic model that adjusts for the same effects. Summary statistics for baseline, follow-

- 989 up, and change from baseline will be reported by study, along with the adjusted differences between the
- studies and their 95% confidence intervals. Boxplots displaying baseline and follow-up for both groups
- 991 will be drawn for continuous outcomes.

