# JAEB CENTER FOR HEALTH RESEARCH

| VERSION
NUMBER | AUTHOR | APPROVER               | EFFECTIVE
DATE | REVISION DESCRIPTION  |  |
|-------------------|--------|------------------------|-------------------|--|--|
|                   |        |                        |                   | • Revised material describing analysis details for various outcomes  |  |
|                   |        |                        |                   | • Added section on insulin metrics   |  |
|                   |        |                        |                   | • Expanded description of comparison with
PEDAP historical control  |  |
|                   |        |                        |                   | Revised Endpoints row of Protocol
Summary table to match Stats chapter
changes.  |  |
|                   |        |                        |                   | Revisions based on JCHR QA review  |  |
| 5.0               | [name] | [name], [name] | 14 FEB 2024       | • Relaxed eligibility criteria to allow
enrollment sooner after T1D diagnosis and
allow current pump users   |  |
|                   |        |                        |                   | • Corrected "Error" text in several TOC
entries by fixing text style in section 6.2   |  |
|                   |        |                        |                   | • Revised Protocol Overview section of
Protocol Summary table to make 3 Day
Visit procedures identical to subsequent
visit procedures, consistent with remainder
of document |  |
|                   |        |                        |                   | • Clarified insulin data needed for system initialization in section 3.2.1   |  |
|                   |        |                        |                   | • Revised section 3.3.4 to allow off-cycle optimization of pump settings   |  |
|                   |        |                        |                   | • Revised section 4.2.1 to describe use of
either Dexcom G6 or G7 CGM
components, making this section consistent
with the rest of the document                                  |  |

\*Version in effect at study initiation

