| 261                      | How to turn on and off Control-IQ technology   |
| 262                      | How to understand when Control-IQ is increasing or decreasing basal rates  |
| 263                      | How to administer a meal or correction boluses   |
| 264                      | • What to do when exercising while using the system  |
| 265                      | • How to enable the sleep function and set the sleep schedule  |
| 266
267               | • The parent will be assessed for understanding of the system interface and how to react to safety/alert messages.   |
| 268                      | The parent will be given a User Guide as a reference.  |
| 269                      | 3.2.1 Determination of Initial of Pump Settings  |
| 270
271               | For participants currently using an insulin pump, the study investigator may choose to enter the existing daily pump settings profiles directly into the web-based UVA Clinician Portal.   |
| 272
273
274        | For participants not currently using an insulin pump or without an established daily pump settings profile, initial pump settings will be determined by the study AI algorithm. This will be achieved by study staff providing the following information to a web-based UVA Clinician Portal:                                    |
| 275                      | • The participant's personal CGM data from approximately two weeks prior to initiating pump use  |
| 276                      | • Entering the participant's average total daily insulin dose  |
| 277                      | Body weight  |
| 278
279               | The recommended pump settings will include daily profile values for basal rate, correction factor, carbohydrate ratio, and sleep activity.   |
| 280
281
282
283 | After the recommended settings are provided, they will be reviewed by a study physician. The study physician may make necessary adjustments for safety prior to confirming that the values are successfully entered into the study pump. Both the AI-recommended and approved settings will be recorded on the Clinician Portal. |
| 284                      | Parents will be instructed that any subsequent changes to the pump profile settings related to insulin   |

delivery must be discussed with the study team prior to implementation.

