# 3.3.2 Subsequent Scheduled Study Visits

The remaining scheduled study visits at 1, 2, 4, 6, and 8 weeks will occur either in-clinic or via videoconference in accordance with the schedule and windows shown in Table 4-1 above.

- Procedures for the scheduled visits will be identical to those described for the 3-Day Visit in section 3.3.1 above—including AI-driven pump settings adjustment—with the following visit-specific variations:
- **•** 8 Week visit:
- There will be no AI-driven study pump settings adjustment, and participants will be switched to the post-study insulin pump or MDI therapy that is desired by the participant's parent/legal guardian.
   For participants who were on MDI at study enrollment, the possibility of
  - switching to a commercially-available insulin pump after study completion should be discussed within the first 1-2 weeks of study pump use, to allow time for planning any required insurance- or prescription-related activities. The primary diabetes care team (outside of the study period) should be involved in this process.
  - Study participants will return study devices as specified in section 4.4 below.

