# 838 Chapter 8: Statistical Considerations

## 839 8.1 Statistical and Analytical Plans

The approach to statistical analysis is summarized below. A detailed statistical analysis plan (SAP) will be written and finalized prior to the start of the study.

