prior PEDAP study. For this analysis, participants from the prior PEDAP study will be limited to those 118

- 119 whose RCT baseline HbAlc values are no more than 0.2 percentage points outside of the range observed
- 120 among the PEDAP-AI participants. Basdine metrics for the PEDAP historical control group will be as
- reported for the PEDAP RCT. 121
- The follow-up period for these comparisons will be the7m and gm weeks of study pump use. For PEDAP-122
- 123 AI participa, ntsthis will be the period from the adjustment of pump settings at the 6-Week visit until the
- end of the day before the 8-Week visit. If the 6-Week visit is missed, data from the 14 days before the 8-124
- Week visit will be used. PEDAP-AI participants will be excluded from these analyses if they miss the 8-125
- 126 Week visit. For the PEDAP historical control group, follow-up metrics will be calculated from the 14
- daysprior to the 56m day after the date of the beginning of study pump use. These data will come from the 127
- RCT phase for those who were assigned to the CLC group and Extension phase for those who were 128
- 129 assigned to the SC group. Participantsmust have spent at least SO% of the time between pump initiation and the end of the follow-up period in closed-loopmode, and provided at least 168 hours of data in both
- 130
- the baseline and follow-up periods for inclusion in analyses. 131
- 132 Baseline insulin metrics will usedata reported from the Diabetes Screening CRF. Insulin data must be
- 133 presenton at least 70% of follow-up days to calculate insulin metrics. The day of the 6-Weekvisit will be
- excluded from the calculation of PEDAP-AI participants' insulin metrics. Calculation of units/kg will use 134
- 135 the weight from the Screening visit only.
- 136 5.7 Analysis \Vindows

137 For any analysis or tabulation that involves HbAlc measured at the Closed Loop Initiation visit, the 138 sample must be collected no earlier than three daysprior to the visit and no later than 21 days after the 139 visit.

140 6 Analysis

141 Analysis of the Hiera rchicalEndpoints 6.1

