- 174 percent confidence interval of the change from baseline will be derived from this test.
- 175 6.2.2 Comparison with PEDAP Hist01ical Control

Comparisons between the PEDAP-AI group and the PEDAP historical control group will be made for all of the hierarchical and secondary efficacy endpoints listed above. Continuous endpoints will be compared between the PEDAP-AI and PEDAP cohorts using a linear model adjusting for the baseline value age at initiation of closed loop use, use of pump or MDI before initiation of closed loop use and clinical center as fixed effects. Binary endpoints will be compared using a logistic model that adjusts for the same effects Summary statistics for baseline, follow-up, and change from baseline will be reported by study along with the adjusted differences between the studies and their 95% confidence intervals.Boxplots displaying baseline and follow, up for both groups will be drawn for continuous outcomes.

- 183 displaying baseline and follow-up for both groups will be drawn for continuous outcomes.
- 184 6.3 Analysis of Exploratory Endpoints

Nop-valueswill be calculated for exploratory analyses. Summary statistics for total daily basal insulin
and total daily bolus insulin will be tabulated for baseline, 8 weeks and change from baseline to 8 weeks.

187 For all other outcomes, summary statistics will be tabulated for 8 weeks. Boxplots for the follow-up

- 188 period will be drawn for all outcomes. Boxplots for baseline will be given for total daily basal insulin and
- 189 total daily bolus insulin. Summary statistics for the final 2-week period will be displayed side-by-side
- 190 with those of the PEDAP historical control group.

1916.4Additional Tabulations and Plots

- 192 Summary statistics will be tabulated by day time (6 00 am 9:59 pm) and night time (10:00 pm 5:59 am)
- during baseline and the 8 weeks of follow-up for each of the continuous CGM-measured outcomes listed
 in 5.2.
- 195 During the trial period, the closed-loop system will include a periodic parameter adjustmentdriven by an
- 196 Al-based Advisor system. Tabulatio, ns 24-hour profile plots and boxplots of the continuous CGM-
- 197 measured outcomes listed in 5.2 will be generated for each of thesix adaptation periods and the two 4-
- 198 week periods of the study.
- 199 The end of the first 4-weekperiod will be the adjustment of pump settings at the 4-Week visit. The end of

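### Protocol 8.10 and SAP 5.6/6.2.2 specify different PEDAP control groups and models; the Protocol version takes no account of enrolled pump users

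*Protocol*

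**What the plan says.** **Control group.** Protocol 8.10 restricts the PEDAP sample to children "who were using MDI before initiating use of the study pump" whose HbA1c lies within 0.2 points of the PEDAP-AI range. SAP 5.6 has the HbA1c condition alone ("whose RCT baseline HbAlc values are no more than 0.2 percentage points outside of the range observed") and no restriction on prior therapy.

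**Model.** Besides the baseline value, Protocol 8.10 adjusts for "age at initiation of closed loop use, and clinical center as fixed effects". SAP 6.2.2 has those terms and adds one; its list ends "use of pump or MDI before initiation of closed loop use and clinical center as fixed effects".

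**Who may enrol.** Protocol 3.2.1 sets out a route "For participants currently using an insulin pump", and Protocol 3.3.2 treats MDI as one case among others ("For participants who were on MDI at study enrollment"). The version 5.0 history entry, which relaxed eligibility to "allow current pump users", shows where this came from; as given, it lists no Chapter 8 edit.

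**Status of the two texts.** Protocol 8.1 says of Chapter 8: "The approach to statistical analysis is summarized below", with a detailed SAP to follow. SAP section 2 declares the SAP consistent with the protocol statistics chapter, in the version named on the SAP title page. That page was not available for this review.

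**Related differences.** SAP 13 has a subgroup by MDI or pump use at enrollment; Protocol 8.19 does not. For controls, Protocol 8.10 counts day 56 from closed-loop initiation, and SAP 5.6 counts it from the start of study pump use.

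**The concern.** Change from baseline in a single-arm study mixes the effect of starting Control-IQ with any effect of the Advisor. The PEDAP comparison is the only place where the plan sets PEDAP-AI against children without AI-driven settings. With external controls, credibility rests on fixing the control definition and the model before the comparison is run.

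Here two definitions are fixed, and they differ. Under Protocol 8.10 a cohort that may mix pump and MDI users is compared with MDI users only, with no term for prior therapy. Any outcome difference between former pump users and former MDI users that remains after adjustment would then be read as an Advisor effect. No text available says which document governs.

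**Working it through.** The plan gives no standard deviation, effect size or control count for this comparison, so there is no figure of its own to reproduce. The text comparison establishes the conflict. The arithmetic below only shows its possible size, and **every numerical input is an assumption** except the 30 PEDAP-AI children, which is the plan's completion goal.

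**Inputs.** 30 PEDAP-AI children; 30-60 MDI controls; residual SD of 6-10 time-in-range points; pump share p in PEDAP-AI of 10-50%; residual pump-minus-MDI gap d of 1-5 points; true Advisor effect zero.

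**1. Bias under Protocol 8.10.** With no pump users among controls and no prior-therapy term, bias ≈ p × d.
- Low: 0.10 × 1 = 0.1 points
- Mid: 0.25 × 3 = 0.75 points
- High: 0.50 × 5 = 2.5 points

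With a gap of 2-8 points instead, the range is 0.10 × 2 = 0.2 to 0.50 × 8 = 4.0 points. If no pump users enrol, the bias is zero.

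**2. Against the standard error.** SE = SD × √(1/30 + 1/n), with n controls: 1.34 (SD 6, n 60), 1.89 (SD 8, n 45), 2.58 (SD 10, n 30).

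| Bias (points) | SE | Bias/SE | Rejection at nominal 5% |
|---|---|---|---|
| 0.1 | 2.58 | 0.04 | 5.0% |
| 0.75 | 1.89 | 0.40 | 6.8% |
| 2.5 | 2.58 | 0.97 | 16.2% |
| 2.5 | 1.34 | 1.86 | 46.2% |

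These rates are before false-discovery-rate control. A simulation of the same four cases (8,000 trials each, adjusting for baseline) gave biases of 0.11, 0.74, 2.51 and 2.50 points and rejection of 5.1%, 7.1%, 14.9% and 43.8%. With the SAP 6.2.2 covariate and 35% pump users among controls, bias was at most 0.01 points in size and rejection was 4.7-5.2%.

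**3. Precision under the SAP model.** Dropping the MDI limit enlarges the control pool. If 35% of eligible PEDAP children were pump users, n MDI controls come with n × 0.35/0.65 pump controls. With a prior-therapy term, the information on the study difference is the sum over the two therapy strata of n₁n₀/(n₁+n₀), where n₁ and n₀ are PEDAP-AI children and controls in the stratum.
- Mid case (p 25%, n 45, so 24.2 pump controls): 22.5×45/67.5 + 7.5×24.2/31.7 = 15.0 + 5.7 = 20.7, against 30×45/75 = 18.0 under Protocol 8.10. SE ratio √(18.0/20.7) = 0.93.
- p 50%, n 30 (16.2 pump controls): 15×30/45 + 15×16.2/31.2 = 10.0 + 7.8 = 17.8, against 30×30/60 = 15.0. Ratio √(15.0/17.8) = 0.92.

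Simulation put the fall in SE at about 4-9%. A small rise (up to about 6%) appears only if both models are given the same number of controls, which is not what the SAP does.

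**4. Why both changes belong together.** Dropping the MDI limit without the covariate leaves a bias of (p − q) × d, where q is the pump share among controls: p 20%, q 60%, d 5 gives −0.40 × 5 = −2.0 points. Adding the covariate but keeping MDI-only controls removes the bias but leaves PEDAP-AI pump users with no counterpart. In simulation (SD 8, 90 PEDAP children before restriction) the SE was then about 2.0-2.5, against about 1.7-1.8 with all controls.

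**The case against.** The strongest reply is that the problem is already solved. The SAP has the wider control group, the covariate and the subgroup, and Protocol 8.1 presents Chapter 8 as a summary. On this view Chapter 8 is simply stale, in a secondary comparison outside the hierarchical tests of an unpowered pilot. Most of that stands. It makes the SAP's answer the natural one and limits the remedy to alignment. It does not remove the conflict: the SAP declares itself consistent with the statistics chapter, and on this comparison it does not match the current one. If the SAP title page names a version other than 5.0, the statement may have been true of that version but does not cover the current text.

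The sizes are also open to challenge. All the key inputs are assumed, and the 16-46% rejection rates need a 50% pump share, a 5-point residual gap and use of the Protocol text.

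A reader might infer more than the documents support:
- *That the analysis as planned is biased.* It is not if the SAP is followed, or if no pump users enrol.
- *That the day-56 wording shifts the control window.* It does so only if pump start and closed-loop start differed in PEDAP. Protocol 3.2 allows open-loop pump use during training in PEDAP-AI; nothing is said about PEDAP, and the dates may coincide.
- *That the baseline for SC-assigned controls is an error.* SAP 5.6 deliberately takes RCT baselines for all controls while taking SC follow-up from the Extension. The resulting lag is a comparability question of unstated length. An assumed mid case (35% SC share × baseline slope 0.45 × 2-point drift) gives 0.32 points, or 0.17 SE.
- *That excluding PEDAP-AI children who miss the 8-Week visit must change.* That is an explicit rule. A calendar window instead could take in days before the 6-Week adjustment, since that visit may fall up to 4 days late.

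**Conclusion.** The concern holds as a conflict between documents. Protocol 8.10 was not brought into line with the enrolment of pump users, and the SAP specifies a different and sounder control group and model. If Protocol 8.10 were followed and pump users enrolled, the adjusted difference would be off by roughly p × d. Under the assumed ranges that is 0.1-2.5 time-in-range points, with a mid case of 0.75 points and about 6.8% rejection. A positive gap would favor PEDAP-AI; a negative one would count against it. Confidence is high on the text and low on the size, because the pump share, gap, SD and control count are not in the documents. The anchor wording is a tidying item with no effect shown. The primary non-inferiority tests and the rest of the hierarchy do not use PEDAP data and are unaffected.

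**What to change.** 1. Amend Protocol 8.10 to the SAP 5.6 control group (all PEDAP participants in the HbA1c band) and the SAP 6.2.2 covariate list. Make both changes together.
2. Add the SAP 13 subgroup by MDI or pump use to Protocol 8.19.
3. Correct the SAP section 2 consistency statement, naming the Protocol version it refers to.
4. While editing, state one day-56 anchor for PEDAP controls in both documents.
5. Optional: keep the RCT baseline as the main definition and add one sensitivity analysis restricted to CLC-assigned controls, applying both the HbA1c band and the baseline adjustment to that subset.

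Items 1-4 are text edits, to be made before the comparison is run; no new data are needed. Item 5 is one extra model run, with a wider interval for that run only. At SD 8, losing 20-50% of an assumed 60 controls raises the SE from 1.79 to between 1.86 and 2.07 (about 4-15%); from an assumed 45 controls the rise is about 5-18%. The main estimate keeps its precision.

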# 8.11 Analysis of Exploratory Endpoints

No p-values will be calculated for exploratory analyses. Summary statistics for total daily basal insulin and total daily bolus insulin will be tabulated for baseline, 8 weeks, and change from baseline to 8 weeks.

995 For all other outcomes, summary statistics will be tabulated for 8 weeks. Boxplots for the follow-up

period will be drawn for all outcomes. Boxplots for baseline will be given for total daily basal insulin and

total daily bolus insulin. Summary statistics for the final 2-week period will be displayed side-by-side

- 998 with those of the PEDAP historical control group.
- 999

992

# 8.12 Additional Tabulations and Plots

Summary statistics will be tabulated by daytime (6:00 am - 9:59 pm) and nighttime (10:00 pm - 5:59 am) during baseline and the 8 weeks of follow-up for each of the continuous CGM-measured outcomes listed in section 8.4.2.

1003 During the trial period, the closed-loop system will include a periodic parameter adjustment driven by an

1004 AI-based Advisor system. Tabulations, 24-hour profile plots, and boxplots of the continuous CGM-

1005 measured outcomes listed in section 8.4.2 will be generated for each of the six adaptation periods and the 1006 two 4-week periods of the study.

## 1007 8.13 Safety Analyses

Hierarchical safety endpoints will be analyzed according to the directions in section 8.8. All safety
endpoints listed in section 8.4.1 will be summarized in tables. Details of each reportable adverse event
will be provided in a listing.

- 1011 8.14 Intervention Adherence
- 1012 The following will be tabulated for the 8-week study period to assess intervention adherence:
- 1013 Percent time of CGM sensor use
- Percent time of closed-loop system use
- 1015 Percent time in different operational modes
- 1016 Percent of AI recommendations that are accepted

# 1017 **8.15 Protocol Adherence and Retention**

1018 The following tabulations and analyses will be performed to assess protocol adherence for the study:

- 1019 Number of protocol and procedural deviations
- Flowchart accounting for all enrolled participants
- Flowchart of all participants at all scheduled visits and phone contacts after treatment initiation
- Number of and reasons for unscheduled visits and phone calls
- Number of participants who stopped treatment and reasons

#### 1024 **8.16 Baseline Descriptive Statistics**

1025 Baseline demographic and clinical characteristics of all participants included in the primary analysis will 1026 be summarized in a table with statistics appropriate to the distribution of each variable.

